5.4. Intervention

We designed the intervention (“Integrated Hypertension and Diabetes Primary Care Model” [*Modelo Integral de Hipertensión y Diabetes en la Atención Primaria*]) based the study team’s prior implementation research projects^{14-16,30,31} and discussions with the MOH and PAHO. Each of the components previously has been tested in the study team’s prior hypertension projects, but the focus on integrated diabetes management is novel in this project. The intervention consists of five HEARTS-aligned components (**Figure 2**). These components together comprise the evidence-based clinical intervention we seek to implement, which we define as: “pharmacological and non-pharmacological treatment of hyperglycemia and hypertension in primary care.”

Figure 2: Intervention components

5.4.1. Training health workers on hypertension and diabetes management

This component includes training on healthy-lifestyle counseling, evidence-based treatment protocols, and risk-based cardiovascular disease management. Training workshops will be conducted for first and second level health workers, including auxiliary nurses, professional nurses, and physicians, to provide instruction in standardized screening, diagnostic, and treatment protocols for hypertension and diabetes in MOH guidelines.^{27,28} Initial workshops will be divided into two blocks, each lasting two days, in the first month of the project. A refresher training session also will be provided in the fourth month of the project. Sessions will be delivered separately at each health district's office headquarters. The sessions will be provided separately. The training will adapt a curriculum previously used in the study team's HEARTS-aligned projects and approved by the Department of Health Training and Education (*Departamento de Promoción y Educación en Salud [PROEDUSA]*), which is the unit in the MOH/SIAS charged with continuing medical education. Workshop content will include the following topics: an introduction to hypertension and diabetes, diagnostic criteria, use of stepped treatment protocols, treatment targets, medication side effects, counseling to promote lifestyle changes, motivational interviewing, team-based care, capture and use of electronic patient data, and other topics. Participants will knowledge assessments before and after training workshops. Of note, MOH treatment targets for diabetes are fasting glucose 70-115 mg/dL, post-prandial glucose 70-160 mg/dL, or HbA1c <7.0; MOH treatment targets for hypertension are <130/80 mm/Hg.^{28,32,33}

5.4.2. Team-based care and task sharing

To implement hypertension and diabetes care in health posts, we will implement a team-based, task-sharing care model between auxiliary nurses staffing health posts and prescribing clinicians (i.e., physicians or professional nurses) at health centers. This intervention component was implemented in the study team's prior hypertension project and has been approved by the MOH.¹⁵ Physicians or professional nurses will make initial patient treatment plans. Auxiliary nurses working in health posts will implement treatment plans by dispensing medications, monitoring glycemic or blood pressure control, and titrating medications under physician supervision. Monthly care coordination meetings will be held in-person or remotely at least once per month to review patient registries and make recommendations for patients whose hypertension or diabetes is not adequately controlled according to MOH guidelines.^{27,28} In our prior projects, monthly meetings have been difficult to operationalize.³⁴ Therefore, we may suggest an alternative approach in which auxiliary nurses at health posts communicate with physicians at health centers in real-time via text messages or phone calls to make treatment changes for uncontrolled patients.

5.4.3. Strengthening access to medications and diagnostics

We have extensive experience collaborating with the MOH to improve medication procurement and logistics at MOH health centers and health posts. In the study team's hypertension project in five departments, nearly 100% availability of key medications was achieved in MOH facilities over a course of three years. In the current project, we will expand the scope to improve access to diagnostics and medications for diabetes at participating MOH primary care facilities. We will coordinate with and train MOH staff on topics that include forecasting demand, seasonal budgeting, storage, shipping, and other topics. The focus will be on a small set of MOH priority medications and diagnostics. Drugs include antihypertensive medications (i.e., hydrochlorothiazide, enalapril, losartan) and oral hypoglycemic agents (i.e., metformin and glimepiride). Diagnostics including blood pressure cuffs and monitors, glucometers, lancets, and glucose strips. As noted in 5.1.2, all medications and diagnostics are provided freely to patients in the MOH. The implementation of a facility-based electronic monitoring tool, described below, also functions to improve available of medications and diagnostics by providing enhanced data to monitor supply and demand at primary care facilities.

5.4.4. Facility-based electronic monitoring tool at the individual level

As described above, there is currently no electronic or paper medical record system in primary care in the MOH system. There is also no registry of patients with diabetes or hypertension, and thus, it is not possible to monitor patient or population data on diabetes or hypertension awareness, treatment, and control in the MOH. To address this gap, the study team previously has collaborated with the MOH to pilot the District Health Information System 2 (DHIS2) in health centers and health posts. DHIS2 is an open-source, facility-based electronic monitoring tool that can monitor key indicators at the individual and aggregate levels.³⁵ We will implement the DHIS2 system including both hypertension and diabetes modules in MOH primary care facilities. Registries of patients with hypertension and diabetes will be constructed at each MOH facilities. The project will provide hardware (e.g., tablets or desktop computers), internet connectivity, technical support, and training and supervision of MOH staff. The DHIS2 system will be hosted on a centralized server, allowing for trained health workers to enter data and monitor patient data in real time. In the WHO classification system for digital health

interventions, this intervention component is a healthcare provider intervention focusing on client health records.³⁶

5.4.5. Systems monitoring and feedback of key indicators

HEARTS requires the use of routine administrative clinical data to monitor key indicators and to iteratively improve the quality of hypertension and diabetes care.³⁷ Each month, we will present aggregate reports of key indicators using data drawn from DHIS2 to MOH stakeholders at the health district (i.e., municipal) and health area (i.e., departmental) levels. The key indicators will be the same as the HEARTS-aligned secondary outcomes described below. We will use a suite of DHIS2 visualization tools built by PAHO, including maps, graphs, and dashboards. In the WHO classification system for digital health interventions, this intervention component is a health system manager intervention focusing on facility management.³⁶ Facility-level monitoring using DHIS2 will be complemented by ongoing health worker training (5.3.1) and site supervision visits (5.3.4).

6. OUTCOMES

6.1. Primary outcomes

Primary outcomes will be feasibility and acceptability as defined in the Implementation Outcomes Framework (**Table 2**).³⁸ These outcomes will be assessed using quantitative data, qualitative data, and mixed methods (integrated qualitative and quantitative data). Given the study team's prior experience with HEARTS-aligned projects, the focus of the feasibility and acceptability assessments will be on integrating diabetes into the HEARTS model.

Feasibility is the extent to which a new intervention can be successfully carried out in an organization.³⁸ Among MOH participants, feasibility will be assessed through the four-item Feasibility of Intervention Measure (FIM) questionnaire³⁹ and semi-structured interviews. Among patient participants, feasibility will be assessed using enrollment data.

Acceptability is the stakeholders' perception that a new intervention is agreeable or satisfactory.³⁸ Among MOH participants, acceptability will be assessed using the Acceptability of Intervention Measure (AIM) questionnaire³⁹ and semi-structured interviews. Among patient participants, acceptability will be assessed using follow-up visit data and semi-structured interviews.

Table 2: Measures of feasibility and acceptability and their benchmarks

Measure	Minimum benchmark
Feasibility	
Feasibility questionnaire (FIM) among MOH participants	Median $\geq 3.5^a$
Reasons for perceptions of feasibility/infeasibility	N/A
Number of patient participants with diabetes enrolled per health district ^b	25
Number of patient participants with hypertension enrolled per health district ^b	25
Acceptability	
Acceptability questionnaire (AIM) among MOH participants	Median $\geq 3.5^a$

Table 2: Measures of feasibility and acceptability and their benchmarks

Measure	Minimum benchmark
Proportion of patient participants with subsequent follow-up visit within 3 months (among those enrolled with ≥ 3 months remaining in pilot)	75%
Reasons for perceptions of acceptability/infeasibility among patient and MOH participants	N/A
Reasons for dropouts among patient participants	N/A
Primary outcomes in this pilot study are feasibility and acceptability as defined in the Implementation Outcomes Framework. ^a The FIM and AIM scales range from 1 to 5 with higher values implying greater feasibility or acceptability, respectively; scores are averaged within each participant. ^b Enrollment is defined by a patient having at least one clinic visit entered in the DHIS2 or equivalent longitudinal medical record system; a given patient may have both diabetes and hypertension and thus count toward each benchmark. Abbreviations: AIM: Acceptability of Intervention Measure; FIM: Feasibility of Intervention Measure; MOH: Ministry of Health.	

6.2. Secondary outcomes

Secondary outcomes include clinical outcomes, implementation outcomes, and patient-related outcome measures (**Table 3**).

Clinical effectiveness outcomes are based on recommended HEARTS monitoring indicators.^{37,40} Clinical outcomes are assessed to provide pilot data to key MOH stakeholders and to rehearse study procedures rather than to evaluate effectiveness.

Implementation outcomes³⁸ will assess facility-level adoption and the fidelity of implementation of each intervention component.

Patient-related outcomes measures relating to diabetes will be conducted to translate and validate questionnaires in Guatemalan Spanish and Mayan Kaqchikel. Measures include diabetes distress, quality of life, and self-care assessments. We will use validated Spanish or professionally translated Mayan language versions of each instrument. These assessments are exploratory to refine the study team's use of these instruments in rural Guatemala.

Table 3: Outcomes and data sources

Outcome	Description and data sources
Primary outcomes	
Feasibility	FIM questionnaires and MOH data from DHIS2 (quantitative); semi-structured interviews with MOH participants (qualitative)
Acceptability	AIM questionnaires and MOH data from DHIS2 (quantitative); semi-structured interviews with patient and MOH participants (qualitative)
Secondary outcomes	
Clinical outcomes	

Table 3: Outcomes and data sources

Outcome	Description and data sources
Number of patients receiving hypertension medication treatment per month (“hypertension treatment rate”)	MOH data from SIGSA (quantitative)
Number of patients receiving diabetes medication treatment per month (“diabetes treatment rate”)	MOH data from SIGSA (quantitative)
Proportion achieving glycemic control (FBG <115 mg/dl or RBG <160 mg/dl) among patients with diabetes	MOH data from DHIS2 (quantitative)
Proportion achieving control of blood pressure (<130/80 mmHg) among patients with hypertension	MOH data from DHIS2 (quantitative)
Mean SBP and DBP among patients with hypertension	MOH data from DHIS2 (quantitative)
Implementation outcomes	
Adoption	Number of participating health facilities, defined as having enrolled at least one patient with hypertension or diabetes (quantitative); reasons for variation (qualitative)
Fidelity (health worker training on hypertension and diabetes treatment protocols)	Proportion of health workers in each district attending all training sessions, chart audit of prescriptions to assess guideline concordance (quantitative); reasons for variation (qualitative)
Fidelity (team-based care and task sharing)	Proportion of primary health districts conducting at least one care coordination meeting; reasons for variation (qualitative)
Fidelity (access to medicines and diagnostics)	Monthly availability of MOH medications and diagnostics (quantitative) and reasons for variation (qualitative)
Fidelity (facility-based electronic monitoring tool)	Proportion of patient visits captured in DHIS2 each month compared to comprehensive records in SIGSA (quantitative) and reasons for variation (qualitative)
Fidelity (systems monitoring and feedback)	Proportion of quarterly reports viewed by health district administrators (quantitative) and reasons for variation (qualitative)
Usability (facility-based electronic monitoring tool)	System Usability Scale ^{41,42} (quantitative) and reasons for variation (qualitative)
Sustainability	Program Sustainability Assessment Tool (PSAT) ^{43,44} and Clinical Sustainability Assessment Tool (CSAT), ^{45,46} select questions

Table 3: Outcomes and data sources

[figure not shown]
Outcome	Description and data sources
Patient-related outcomes measures	
Diabetes distress	Diabetes Distress Scale (DDS), ^{47,48} 2-item screening and physician distress subscale
Disability	WHO Disability Assessment Schedule (WHODAS 2.0) ⁴⁹
Multimorbidity treatment burden	Multimorbidity Illness Perceptions Scale (MULTIPleS), ^{50,51} treatment burden subscale

Abbreviations: CSAT: Clinical Sustainability Assessment Tool; DBP: diastolic blood pressure; DHIS2: District Health Information System; FBG: fasting blood glucose; MOH: Ministry of Health; PSAT: Program Sustainability Assessment Tool; RBG: random blood glucose; SBP: systolic blood pressure; SIGSA: Health Management Information System; WHO, World Health Organization.

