7.4. Data collection and management

Data will be collected using different collection methods.

- Clinical data from patient participants will be entered into DHIS2 by MOH health workers who provide standard clinical care during routine visits. DHIS2 data are stored on INCAP's server, as approved by the MOH.
- Data from structured assessments will be collected electronically using a cloud-based version of REDCap hosted at INCAP. Structured assessments include health facility monitoring, chart audits, and questionnaire data from closing interviews with patients and MOH staff. Data entry and quality control checks will be performed by study staff on all structured data entered into REDCap
- Qualitative data from semi-structured interviews will be collected in the field by a trained qualitative researcher on the study team. Other qualitative data will include field notes, meeting notes, and study team reflections implementation progress and challenges.⁶¹ Qualitative data will be securely stored on the University of Michigan's institutional Dropbox account with routine back-ups to an encrypted hard drive.

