Loss of confidentiality risks: There is the unlikely risk of accidental disclosure of confidential data. Currently, Guatemala does not have a specific national regulation on electronic medical records or telemedicine cybersecurity.⁷¹ To protect against breach of confidentiality, all non-clinical patient data will be maintained using a unique study identification. Structured data will be securely collected using REDCap on an encrypted tablet and stored on INCAP's secure cloud server. Qualitative data from semi-structured interviews will be collected using an encrypted mobile device and stored on the University of Michigan's institutional Dropbox account. An electronic spreadsheet with the unique identification numbers will be maintained on the U-M's institutional Dropbox account, and only the PI and study coordinators will have access. Clinical patient data usually will be entered into the DHIS2 tool by MOH staff during routine clinical visits. Some MOH primary facilities may choose an asynchronous strategy in which patient data are collected using paper records and entered into DHIS2 after the routine clinical visit. These paper forms will be stored in a locked filing cabinet in a locked room at the MOH facility. The DHIS2 system will be hosted on an INCAP's secure cloud server. Password-access to DHIS2 will be restricted to relevant MOH staff, the PI, and study coordinators.

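### The 75% patient follow-up benchmark is read from DHIS2, and no visible section deals with return visits that were made but not entered

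*Combined protocol and SAP*

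**What the plan says.** Section 6.1 sets out the patient side of this co-primary outcome: "Among patient participants, acceptability will be assessed using follow-up visit data and semi-structured interviews". The only patient measure of acceptability with a numerical benchmark in Table 2 is "Proportion of patient participants with subsequent follow-up visit within 3 months (among those enrolled with ≥ 3 months remaining in pilot"), with a minimum of 75%.

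Table 3 (section 6.2) lists the quantitative sources for acceptability as "AIM questionnaires and MOH data from DHIS2 (quantitative"). Section 6.1 assigns the AIM to MOH participants, which leaves DHIS2 for patients.

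DHIS2 is a component of the intervention (section 5.4.4), and its use by staff is evaluated. Table 3 includes the fidelity outcome "Proportion of patient visits captured in DHIS2 each month compared to comprehensive records in SIGSA (quantitative) and reasons for variation (qualitative"). Section 7.4 says who enters the data: "Clinical data from patient participants will be entered into DHIS2 by MOH health workers who provide standard clinical care during routine visits". Section 11.3 adds: "Some MOH primary facilities may choose an asynchronous strategy in which patient data are collected using paper records and entered into DHIS2 after the routine" visit.

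Three activities touch on data quality:
- a weekly data manager review of newly entered DHIS2 data (7.3.6);
- a clinical audit of at least a quarter of patient visits (7.3.6);
- a monthly facility visit that includes a review of patient registration (7.3.2).

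Section 9 does not mention the capture proportion in connection with the 75% measure.

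**The concern.** A patient who comes back within 3 months but has no return visit entered is counted as not having come back. The measure then mixes two things: whether patients return, and whether staff record that they did. Among enrolled patients, missed entries of return visits push the figure in one direction only, downward.

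The described checks do not close the gap. The weekly review looks at data already in the system. The clinical audit rates care and the adequacy of data entry, and is not described as a search for visits with no entry. The monthly visit is described as reviewing registration, not return visits. The footnote to Table 2 that accepts an equivalent record system applies to enrollment only.

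Results feed scale-up planning (section 12). Patients not returning and staff not entering visits are different barriers and call for different strategies. The 75% measure alone cannot tell them apart.

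**Working it through.** **No plan figure to reproduce.** The 75% benchmark is stated without a derivation, and no expected capture or visit frequency is given.

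**Inputs**
- Benchmark: 75% (Table 2).
- Target sample: about 100 patients (section 8).
- True return proportion *r*: not stated; 85% assumed, as a value comfortably above the benchmark.
- Capture per visit *c*: not stated; range assumed.
- Return visits per returning patient in the window *k*: not stated; 1 or 2 assumed.

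**Step 1. Measured proportion.** A returning patient is missed only if every return visit in the window goes unentered. With independent misses:

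measured = *r* × [1 − (1 − *c*)^*k*]

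| Capture *c* | One return visit | Two return visits |
|---|---|---|
| 90% | 0.85 × 0.90 = 76.5% | 0.85 × 0.99 = 84% |
| 80% | 0.85 × 0.80 = 68% | 0.85 × 0.96 = 82% |
| 70% | 0.85 × 0.70 = 59.5% | 0.85 × 0.91 = 77% |

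With one return visit the measured figure is below 75% at 80% capture. With two it stays above 75% even at 70% capture.

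**Step 2. True return needed to measure 75%** = 0.75 / [1 − (1 − *c*)^*k*].
- One visit: 83.3% at *c* = 0.90, 93.8% at 0.80 and 100% at 0.75. Below 75% capture the benchmark cannot be met in expectation.
- Two visits: 75.8% at 0.90, 78.1% at 0.80 and 82.4% at 0.70.

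**Step 3. Chance of meeting the benchmark.** If 100 patients accrue evenly over 6 months, about 50 enroll with at least 3 months left, and 38 or more must be recorded as returning. Exact binomial probabilities for *r* = 85% and one return visit:

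| Capture | 100% | 95% | 90% | 85% | 80% |
|---|---|---|---|---|---|
| P(pass), 50 eligible | 97% | 85% | 61% | 34% | 14% |

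**Step 4. Clustering.** The two-visit column relies on misses being independent. At the other extreme, if some facilities enter all return visits and others none, a second visit gives no protection. The measured figure is then 0.85 × *c* whatever *k* is, for example 0.85 × 0.80 = 68%. Entry practice may differ between facilities (section 11.3), so the truth may lie between the two columns.

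**The case against.** The case on the other side has force on several points.

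- **A reader might infer that the plan expects DHIS2 to be incomplete.** It does not say so. Table 3 gives every intervention component a fidelity measure, and measuring capture is not predicting that it will fail.
- **A reader might take the paper-first option as evidence of lost visits.** Section 11.3 describes delayed entry with the forms kept at the facility. Late entry is not lost entry.
- **A reader might infer that a clear pass will turn into a fail.** That needs assumed capture and either one return visit or clustered misses. Section 5.4.2 has health posts dispensing, monitoring and titrating, so several visits in 3 months are plausible, though no frequency is stated. Patients in the denominator already have one visit entered, so their capture may be better than average.
- **A reader might infer that interviewees will be misclassified.** Sections 7.2 and 8 select on the number of visits but do not name DHIS2 as the source, so this is possible, not established.
- **Poor entry might not pass unnoticed.** The plan collects monthly capture, usability scores, reasons for dropout and interviews, and integrates the primary-outcome findings in joint displays (section 9).
- **Unseen material.** The follow-up facility assessment and chart audit forms (section 15) are not visible, and either could contain a relevant check.

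All of this limits what can be claimed about size and consequence. It does not remove the gap. Dropout reasons and about 10 interviews, all with patients who have diabetes, do not correct the proportion, and no visible section ties capture to the benchmark.

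**Conclusion.** The point holds in a limited form. A benchmarked co-primary measure depends on a record system whose completeness is itself under evaluation, and the visible plan has no rule for return visits that were made but not entered. For enrolled patients such omissions can only lower measured acceptability.

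The size cannot be known from the documents. Under the assumed 85% true return, the shortfall runs from about 1 percentage point (90% capture, two independent visits) to 25.5 points (85 − 59.5; 70% capture, one visit). A wrong fail is mainly a risk with a single return visit or with misses concentrated in some facilities. The documents do not support saying that it will happen.

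This is a single-arm pilot with descriptive benchmarks. The gap does not undermine the design, but it is worth closing because the remedy is cheap and the result informs scale-up.

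**What to change.** Add to section 6.1 and Table 2, with a matching line in 7.3.2:

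1. At the monthly facility visits, study staff check each apparent non-returner against any facility record that can be matched to that patient: paper forms where they are used, and SIGSA entries where matching is possible. Section 5.2.2 says SIGSA was not built to follow patients over time, so it may often not match.
2. Report the DHIS2-only and verified proportions side by side, by facility, with the capture proportion already being collected and the number of non-returners who could not be checked.
3. State that a DHIS2-only result below 75% will not be read as low patient acceptability where capture is low.
4. Use the verified visit count, where available, when choosing high- and low-visit interviewees.

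**Cost.** Protocol wording and a short list at visits already scheduled. With about 50 eligible patients, the scenarios above leave roughly 8 names (50 × 0.16) to 20 (50 × 0.405) to check in total. The downside is a little staff time, and verification that is incomplete and differs by facility. Sites that enter data in real time may have no other matchable record, which is why the unchecked number should be reported.

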7.3.5. Technical Advisory Committee meetings

We will establish a Technical Advisory Committee to provide high-level coordination with national authorities, as recommended in the HEARTS implementation guide.²² The Technical Advisory Committee will play a critical role to provide guidance and to plan for future scale-up. Members will likely include MOH administrators at the national, departmental, and health district levels; physicians and professional nurses working in each health district, representatives of the Guatemalan PAHO office, and other stakeholders (10-15 total members). Study staff at INCAP will organize meetings every two months during the trial and a post-trial closing meeting. Meetings will be conducted virtually and will be recorded for members who cannot attend a given session. Written meeting notes also will be shared after each session.

During the meetings, study staff will present project updates for open discussion. Using an implementation mapping approach,⁵⁴ members then will discuss the implementation determinants (i.e., barriers and facilitators) that emerge during the trial, design implementation strategies to address these determinants, clarify the causal mechanisms through which implementation strategies operate, and provide feedback on a consolidated implementation package the study team creates after the trial concludes. Study staff will guide discussions of implementation strategies using different structured tools:

- The Expert Recommendations for Implementing Change (ERIC) compilation and prior mappings of ERIC to lower-middle-income countries will be used as a foundation for proposed implementation strategies.^{55,56}
- Guidance from Proctor et al. will be used to specify implementation strategies.⁵⁷
- The APEASE (acceptability, feasibility, effectiveness, cost-effectiveness, side effects or unintended consequences, safety, and equity) tool will be used to prioritize implementation strategies.⁵⁸

- Causal pathway models will be presented to link implementation strategies, mechanisms, and key implementation outcomes.^{59,60}

7.3.6. *Chart audits*

Each week, a data manager will review all new data entered into the DHIS2 system for missingness and errors. Physicians on the study team also will perform a clinical audit of at least 25% of patient visits. The physicians will use a structured checklist to rate the guideline-concordance of clinical care and adequacy of data entry.

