10. DATA AND SAFETY MONITORING PLAN

10.1. Adverse event reporting

Because the proposed research is considered no more than minimal risk, adverse events (AEs) related to the proposed strategies are not anticipated. The intervention in this study is focused on improving standard-of-care treatment of diabetes or hypertension delivered by the MOH health workers in MOH facilities. Therefore, it will be the responsibility of the MOH staff to provide care for patient participants who experience an adverse event (e.g., hypotension, hypoglycemia, or other adverse drug effects as noted in 11.3) to manage these patients according to MOH protocols. In our reporting role, the study team will review from MOH records

all serious AEs, unanticipated problems, and other reportable information or occurrence (ORIO) using an event form and reported using to the University of Michigan IRB using the standard timetable and grading scale, consistent with federal guidelines.⁷⁰

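### Table 3 counts a fasting glucose below 70 mg/dL as glycemic control although the MOH fasting target starts at 70, and the protocol body does not link such readings to the monthly adverse event assessment

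*Combined protocol and SAP*

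**What the plan says.** Table 3 in section 6.2 takes this outcome from DHIS2: "Proportion achieving glycemic control (FBG <115 mg/dl or RBG <160 mg/dl) among patients with diabetes". Neither cutoff has a lower bound.

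Section 5.4.1 states the targets that health workers are trained to use: "MOH treatment targets for diabetes are fasting glucose 70-115 mg/dL, post-prandial glucose 70-160 mg/dL", with HbA1c below 7.0 as a further alternative. For blood pressure it says "MOH treatment targets for hypertension are <130/80 mm/Hg".

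Section 5.4.5 uses the clinical outcomes during the trial: "Each month, we will present aggregate reports of key indicators using data drawn from DHIS2 to MOH stakeholders", and "The key indicators will be the same as the HEARTS-aligned secondary outcomes described below".

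Four provisions bear on what happens to a low reading:
- **7.3.6, weekly review:** "a data manager will review all new data entered into the DHIS2 system for missingness and errors".
- **7.3.6, physician audit:** a "clinical audit of at least 25% of patient visits", rating guideline concordance and adequacy of data entry.
- **10.1:** MOH staff manage adverse events. From MOH records the study team reviews "all serious AEs, unanticipated problems, and other reportable information or occurrence (ORIO").
- **10.2:** the study team assesses adverse events monthly, among other items. No data source is named.

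In addition, 5.4.2 has care coordination meetings that go through the patient registries and consider patients not adequately controlled under MOH guidelines.

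**The concern.** Hypoglycemia is named as a possible adverse event in 10.1 and 11.3, and glimepiride is one of the two glucose-lowering drugs in use. Table 3 contains no other glycemic outcome, and this one cannot separate a patient brought from 150 to 100 mg/dL fasting from one brought from 150 to 55. Both move from uncontrolled to controlled.

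MOH stakeholders see the indicator every month, and section 6.2 says that the clinical outcomes are there to give them pilot data and to rehearse procedures. If low readings stay inside the control rate, the pilot hands on an indicator that cannot show overtreatment, and the link from a low reading to adverse event assessment goes unrehearsed before scale-up.

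**Working it through.** **1. Definition against target**

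| Measure | Table 3 outcome | MOH target (5.4.1) | Same lower bound? |
|---|---|---|---|
| Fasting glucose | below 115 mg/dL | 70-115 mg/dL | No |
| Random / post-prandial glucose | random below 160 mg/dL | post-prandial 70-160 mg/dL | Different measurements |
| Blood pressure | below 130/80 mmHg | below 130/80 mmHg | Yes (none in either) |

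The mismatch is exact for fasting glucose. For the second row it is not, because the MOH range is post-prandial and Table 3 uses random glucose. Blood pressure shows no mismatch.

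**2. Denominator**

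Section 8 expects 45 patients with hypertension only, 45 with diabetes only and 10 with both. 45 + 45 + 10 = 100 reproduces the stated target of about 100. Patients with diabetes: 45 + 10 = 55, or 27-28 per district if split evenly.

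**3. Weight of one low reading**

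Assume one classifying reading per patient. Each patient with a fasting reading below 70 adds 1/55 = 1.8 points to the gap between the reported control rate and the share within the MOH fasting range. In a district report it adds 1/28 = 3.6 to 1/27 = 3.7 points.

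Illustration, with assumed counts and all classifying readings fasting: if 22 of 55 (40.0%) meet the Table 3 rule and 3 of them are below 70, then (22 - 3)/55 = 34.5% are in range, a gap of 5.5 points. For 1 to 5 such patients the gap is 1.8 to 9.1 points.

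**4. How many to expect**

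The documents give no rate. If a proportion p of the 55 patients has a classifying reading below 70, the expected number is 55p and the chance of at least one is 1 - (1 - p)^55:

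| Assumed p | Expected patients | Chance of at least one |
|---|---|---|
| 1% | 0.55 | 42% |
| 2% | 1.1 | 67% |
| 5% | 2.75 | 94% |
| 10% | 5.5 | 99.7% |

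**5. Tracing the routes to the 10.2 assessment**

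- The weekly review looks for missing values and errors. A true low reading is neither.
- The audit would show low readings in the visits it covers, but no handover to 10.2 is stated.
- Section 10.1 could pick up a severe event. A low meter value alone is not said to trigger it.
- The registry review in 5.4.2 could find a patient below 70 as outside the MOH target. It leads to treatment recommendations, not to adverse event assessment, and 5.4.2 says that these meetings have been hard to run.

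Coverage of the audit, under assumptions: with 220 glucose readings (55 x 4), 4 of them low, and 55 (25%) audited at random, the chance that none of the 4 is audited is C(216,55)/C(220,55) = 0.31. With 110 audited it is 0.06. At exactly 25% audited it is about 0.75 for 1 low reading in 110, and below 0.01 for 17 in 330. The result depends almost wholly on the assumptions.

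**6. Load of a weekly list**

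At 220 readings and 2% low: 220 x 0.02 = 4.4 over 26 weeks, or 0.17 per week. The range runs from 110 x 0.01 = 1.1 (0.04 per week) to 330 x 0.05 = 16.5 (0.63 per week).

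**The case against.** The strongest reply is that safety review is already planned. Section 10.2 assesses adverse events every month, 10.1 draws on MOH records, physicians audit at least a quarter of visits, 5.4.2 reviews whole registries, staff are trained on medication side effects, and study staff visit each facility monthly. The DHIS2 visit forms, follow-up facility assessments and chart audit form are listed as supplementary files and may hold the missing detail. Much of this stands. A reader might infer that low readings have no way to reach the study team; the documents do not support that. They show only that the protocol body states no link from a low DHIS2 reading to the 10.2 assessment.

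A second reply is that the outcome is secondary, is not meant to evaluate effectiveness, and follows recommended HEARTS indicators. That limits the priority. It does not remove the mismatch, because the protocol's own fasting target has a lower bound and the indicator is fed back monthly.

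A third is that the size rests on assumed rates. That is correct: only the 1.8 points per patient follows from the planned numbers.

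A reader might also infer that supervised titration by auxiliary nurses raises the risk of hypoglycemia. Section 5.2.2 says drug management is not typically their role, but 5.4.2 describes task sharing as used in the prior hypertension project and approved by the MOH. Nothing in the documents shows a higher risk.

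**Conclusion.** The definitional point holds on the text: a fasting reading below 70 mg/dL is outside the MOH target and is scored as control in Table 3 and in the monthly report. Each such patient is worth 1.8 points of 55, assuming the planned mix and one classifying reading per patient. The total cannot be estimated, because no rate of low readings is given.

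It would go too far to say that the control rate is inflated by every low reading. A low reading raises the rate only for a patient who would otherwise be above the cutoff; for others it is merely hidden within the rate. Nor can the lower limit of 70 simply be carried over as a target for random readings.

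The reporting point holds in a narrower form. The link to 10.2 is not stated in the protocol body; whether the forms supply it is unknown.

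This is a low-priority improvement. The Table 2 benchmarks and the sample size do not change.

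**What to change.** 1. Keep the Table 3 control indicator as it is. Beside it, in the monthly 5.4.5 report and the final report, give the number of glucose readings and the number of patients below 70 mg/dL. A count below 70 needs no fasting or meal-time label, so it works for both reading types.
2. State next to the count that it covers readings at clinic visits only. A zero would not exclude hypoglycemia between visits. Even for visit readings, 0 of 55 patients leaves an exact two-sided upper 95% limit of 1 - 0.025^(1/55) = 6.5%.
3. Add one sentence to 7.3.6 or 10.2: the weekly DHIS2 review also lists glucose readings below 70 mg/dL, and the list goes to the monthly adverse event assessment. Clinical management stays with MOH staff as in 10.1.

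The cost is one filter in a review that already runs and one line in a report that already goes out. Glucose values must already be in DHIS2, since Table 3 takes the control outcome from there, so no new data, visits or staff are needed. The downside is a few entries to check, fewer than one per week on average under the assumed ranges. Some may prove to be entry errors, which the same review is meant to find.
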